APPENDIX 10. INTERNATIONALLY AGREED ORDER FOR SYSTEM ORGAN CLASS

Internationally Agreed Order

Infections and infestations
Neoplasms benign, malignant and unspecified (incl cysts and polyps)
Blood and lymphatic system disorders
Immune system disorders
Endocrine disorders
Metabolism and nutrition disorders
Psychiatric disorders
Nervous system disorders
Eye disorders
Ear and labyrinth disorders
Cardiac disorders
Vascular disorders
Respiratory, thoracic and mediastinal disorders
Gastrointestinal disorders
Hepatobiliary disorders
Skin and subcutaneous tissue disorders
Musculoskeletal and connective tissue disorders
Renal and urinary disorders
Pregnancy, puerperium and perinatal conditions
Reproductive system and breast disorders
Congenital, familial and genetic disorders
General disorders and administration site conditions
Investigations
Injury, poisoning and procedural complications
Surgical and medical procedures
Social circumstances
Product issues

Document:

CCI

Author:

PPD

Version Number:

0.6

Version Date:

30JAN2023

Template No.: CS_TP_BS016 Revision 6

Reference: CS_WI_BS005

Effective Date: 02Dec2019

APPENDIX 11. IDENTIFICATION OF SUICIDALITY, HOMICIDALITY, AND/OR RISK OF HARM TO SELF OR OTHERS

Condition	Data Source	Criteria
Suicidality or Risk of Harm to Self	Adverse events	
 AEs with preferred term of “Assisted suicide”, “Completed suicide”, “Suicide attempt”, “Suspected suicide”, or “Suspected suicide attempt” Medical review of all AEs contained in the MedDRA SMQ of “Suicide/self-injury (SMQ)”
	C-SSRS	
 C-SSRS findings of at least one occurrence of suicidal ideation (Item 4 and/or Item 5) or at least one occurrence of suicidal behavior C-SSRS findings of self-injurious behavior, defined as a “Yes” answer to the following question in the Suicidal Behavior section: Has subject engaged in Non-Suicidal Self-Injurious behavior?
Homicidality or Risk of Harm to Others	Adverse events	
 AEs with preferred term of “Aggression”, “Anger”, “Antisocial behaviour”, “Belligerence”, “Defiant behaviour”, “Homicide”, “Homicidal Ideation”, “Hostility”, “Physical abuse”, “Physical assault”, or “Violence-related symptom” contained in the MedDRA SMQ of “Hostility/aggression (SMQ)” AEs with a verbatim term that contains text of “homicid*”, “kill*”, or “murder*”.

Document: CCI

Author: PPD

Version Number: 0.6

Version Date: 30JAN2023

Template No.: CS_TP_BS016 Revision 6

Reference: CS_WI_BS005

Effective Date: 02Dec2019

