16.2.12. RELAPSE

Relapse is defined as the earliest occurrence of any of the following:

- Worsening of >30% PANSS total score from Baseline (Day 1) and a CGI-S score >3
- Hospitalization for worsening of psychosis
- Emergence of suicidality, homicidality and/or risk of harm to self or others
- Discontinuation from the study due to exacerbation of the underlying illness of schizophrenia.

PANSS and CGI-S assessments taken at both scheduled and unscheduled visits will be considered when identifying the relapse event. The percent change in PANSS total score from Baseline will be calculated as described in [Section 16.1.6](#). Occurrence of hospitalization for worsening of psychosis will be identified by medical review of the data collected on the “*Psychiatric Hospitalization*” CRF page as well as the SAEs prior to database lock. Emergence of suicidality, homicidality, and/or risk of harm to self or others will be identified as outlined in [APPENDIX 11](#). Discontinuation from the study due to exacerbation of the underlying illness of schizophrenia will be identified as an AE included in the SMQ search listed in [APPENDIX 13 that has action taken = “Drug Withdrawn”](#).

The evaluation period for relapse will be from the day of the first dose of study medication to 2 days after the day of the last dose of study medication.

The date of relapse is defined as the earliest of: the start date of the assessment at which the qualifying PANSS and CGI-S data were collected, the date of hospital admission for worsening of psychosis, the

Document: **CCI**

Author: **PPD**

Version Number: 0.6

Version Date: 30JAN2023

Template No.: CS_TP_BS016 Revision 6

Reference: CS_WI_BS005

Effective Date: 02Dec2019

date of the assessment at which a qualifying C-SSRS event is identified, the start date of the qualifying adverse event for the second and third criteria, and the last dose date for the fourth criterion.

Time-to-relapse (in days) is defined as the date of relapse – the first dose date + 1. Subjects completing/discontinuing from the study without meeting the criteria for relapse will be censored on 2 days after the last dose of study medication.

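### Appendix 11 of the SAP counts non-specific adverse events such as Anger or Hostility as relapse on the coded term alone, with no severity condition or stated medical review

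*SAP*

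**What the plan says.** SAP 16.2.12 makes relapse a composite: "Relapse is defined as the earliest occurrence of any of the following". The third component is "Emergence of suicidality, homicidality and/or risk of harm to self or others". The same section leaves its detection to an appendix: "Emergence of suicidality, homicidality, and/or risk of harm to self or others will be identified as outlined in" Appendix 11.

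The harm-to-others row of Appendix 11, headed "Homicidality or Risk of Harm to Others", uses adverse event data only, under two rules:

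- A term list: "AEs with preferred term of “Aggression”, “Anger”, “Antisocial behaviour”, “Belligerence”, “Defiant behaviour”, “Homicide”, “Homicidal Ideation”, “Hostility", followed by Physical abuse, Physical assault and Violence-related symptom. All eleven terms are drawn from the Hostility/aggression SMQ.
- A string search: "AEs with a verbatim term that contains text of “homicid*”, “kill*”, or “murder".

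Neither rule has a condition on severity, seriousness or action taken, and neither mentions review.

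The self-harm row counts five suicide terms directly. It then adds "Medical review of all AEs contained in the MedDRA SMQ of “Suicide/self-injury (SMQ", restricts C-SSRS ideation to items 4 and 5, and accepts any C-SSRS suicidal behavior or a positive answer on non-suicidal self-injury.

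Under 16.2.12 the evaluation window runs from the day of first dose to 2 days after last dose. A relapse identified from an adverse event under the third criterion is dated at that event's start. The results feed Kaplan-Meier estimates, a log-rank test between arms and a relapse rate with a 95% confidence interval.

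**The concern.** Protocol 6.3 words the third criterion as ideation of suicide or homicide, or risk of harm to self or others. Anger, defiance or belligerence alone is neither homicidality nor danger to another person. Protocol 12.3 grades as mild those events that usually pass and leave daily activities unaffected, and such events are recorded and coded like any other. A subject with one mild Anger event in Week 3 who then completes 52 weeks on drug would therefore be a Week 3 relapse.

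Two errors follow. Subjects who never relapsed become events, and subjects who relapse later are dated too early if such an event came first. If these adverse events occur at different rates in the two arms, part of the log-rank comparison would reflect irritability rather than relapse.

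**Working it through.** The plan states no figure that bears on this point, so there is nothing to reproduce. The check is a comparison of the text, followed by an illustration.

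**How each broad adverse-event route to relapse is filtered**

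| Route | Source | Filter |
|---|---|---|
| Hospitalization for worsening psychosis | SAP 16.2.12 | Medical review of the CRF page and SAEs before database lock |
| Exacerbation (psychosis SMQ) | SAP 16.2.12, Appendix 13 | Action taken must be Drug Withdrawn |
| Suicide/self-injury SMQ | Appendix 11 | Medical review |
| Harm to others: 11 terms | Appendix 11 | None stated |
| Harm to others: text strings | Appendix 11 | None stated |

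Of the eleven terms, six fit the criterion on their face: Aggression, Homicide, Homicidal ideation, Physical abuse, Physical assault and Violence-related symptom. The other five (Anger, Antisocial behaviour, Belligerence, Defiant behaviour, Hostility) do not settle whether anyone was at risk. The string rule is also loose. Read literally, a verbatim term that mentions a painkiller contains the kill string.

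**Illustration.** The rates are assumptions, not document figures. Planned arm sizes follow from 300 subjects at 2:1 (SAP 3.4): 200 on SEP-363856 and 100 on quetiapine XR. The efficacy population, which is the denominator of the relapse rate, may be smaller.

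Let r be the true relapse rate and q the share of the remaining subjects who have a non-specific listed event. Then observed rate = r + (1 − r)q. With r = 20% in both arms:

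| q | Observed rate | Added relapses, n = 200 | Added relapses, n = 100 |
|---|---|---|---|
| 1% | 20.8% | 1.6 | 0.8 |
| 2% | 21.6% | 3.2 | 1.6 |
| 5% | 24.0% | 8 | 4 |
| 10% | 28.0% | 16 | 8 |

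For example, at q = 2%: 0.20 + 0.80 × 0.02 = 0.216, and 200 × 0.80 × 0.02 = 3.2.

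Now suppose true rates of 15% (SEP-363856) and 25% (quetiapine XR), with the same q in both arms. The observed risk ratio is (0.15 + 0.85q)/(0.25 + 0.75q). Power is for a two-sided 5% comparison of two proportions by normal approximation, with pooled variance under the null. At q = 0 the pooled rate is 55/300 = 0.183, the null standard error 0.0474 and the alternative standard error 0.0501. So z = (0.10 − 1.96 × 0.0474)/0.0501 = 0.142, and power is 55.6%.

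| q | Risk ratio | Power |
|---|---|---|
| 0 | 0.60 | 55.6% |
| 1% | 0.62 | 53.6% |
| 2% | 0.63 | 51.6% |
| 5% | 0.67 | 46.2% |
| 10% | 0.72 | 38.7% |

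Equal contamination pulls the comparison toward no difference. Unequal contamination can push it either way: with r = 20% in both arms and q = 5% in only one, the observed rates would be 24.0% and 20.0% with no true difference.

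**The case against.** There is a fair case for the rule as it stands.

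- **Manual review is already in the protocol.** Protocol 15.3.5 says relapse will be found by program and by manual data review, and SAP 3.7 does not withdraw this. A reader might infer from Appendix 11 that no human looks at these cases; the documents do not support that. But the manual review applies the pre-defined criteria, and a listed term is one of them, so the reviewer has no stated ground for rejecting a mild Anger event.
- **The two rows differ less than they seem.** A reader might infer that the self-harm row is fully reviewed. It is not: the five suicide terms, C-SSRS suicidal behavior and non-suicidal self-injury all count without stated review. Those items, however, bear directly on the self-harm criterion, which Anger or Defiant behaviour does not do for harm to others.
- **The list is a selection.** Naming eleven terms from an SMQ is a recognised and reproducible alternative to reviewing the whole SMQ. That holds for the six specific terms. For the other five, a term alone cannot separate irritability from danger.
- **The consequences are limited.** Protocol 15.3.5 calls all efficacy analyses exploratory, SAP 7.4 reports nominal p-values, and the sample size does not rest on relapse. This stands and bounds the importance of the point.

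**Conclusion.** The point holds for the five non-specific terms and the text matches. As written, they make an adverse event a relapse, dated at its onset, without any test of whether homicidality or risk to others was present. What is affected is the relapse rate, the time-to-relapse estimates and the log-rank test.

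Three stronger readings are not supported. The fault does not extend to all eleven terms. It does not reach events at any time, because the window closes 2 days after last dose. And it does not show that the arm comparison is biased: nothing in the documents says these events are common or differ by arm, and the primary adverse event endpoint does not use this rule.

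The size cannot be computed from the documents. The figures above rest on assumed true relapse rates (20%, or 15% against 25%), on an assumed q of 1% to 10%, and on the planned arm sizes. The change is still worth making: maintenance efficacy, including time to and rate of relapse, is a stated objective, and the correction is cheap.

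**What to change.** Amend the harm-to-others row of Appendix 11 as follows:

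1. Keep as direct criteria the terms that plainly meet the definition: Homicide, Homicidal ideation, Physical assault, Physical abuse and similar. Aggression and Violence-related symptom can reasonably stay with them.
2. Treat Anger, Antisocial behaviour, Belligerence, Defiant behaviour and Hostility, together with the verbatim string matches, as a search list. Count such an event only when blinded medical review before database lock confirms homicidality or risk of harm to others.
3. Report a sensitivity analysis of relapse rate and time to relapse with every listed term and string counted as Appendix 11 now has it.

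The cost is a few more records in a medical review that SAP 16.2.12 already places before lock for hospitalizations, a short change to Appendix 11 and one repeated analysis. It brings in a small element of judgement, made blind to treatment and of the kind the plan already accepts for the Suicide/self-injury SMQ. The sensitivity analysis shows how much turns on it.

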APPENDIX 12. CLASSIFICATION OF PATIENT TYPE FROM UPSM FACTOR SCORES

Guided machine learning via linear support vector machine (L-SVM) algorithm in MATLAB will be used to classify subjects into 5 patient types based on UPSM factor scores. There are 5 distinct patient types described in the table below.

• TYPE	• PATIENT TYPE
• 1	• Prominently Disorganized
• 2	• Prominently Negative
• 3	• Prominently Hostile
• 4	• Prominently Positive
• 5	• Prominently Affective

The classification will occur in two steps:

Step 1: Train L-SVM in MATLAB to classify subjects into 1 of 5 patient types using 7 columns of UPSM data. Training dataset is given in the table below.

Step 2: Use the now trained classifier function in MATLAB to classify subjects into 1 of 5 patient types using 7 columns of UPSM data.

Table 8: Training Dataset

UPSM-HOS	UPSM-DIS	UPSM-POS	UPSM-NAA	UPSM-ANX	UPSM-NDE	UPSM-DEP	TYPE
0.110138	1.960813	0.478927	3.298293	1.382828	2.114771	0.391504	1
1.431769	1.616874	3.310726	2.225812	0.541127	1.542821	0.22721	4
0.537462	2.293898	3.358519	2.713077	2.582309	1.584137	2.762624	5
1.458801	0.51371	3.162632	4.179415	2.367169	0.687056	2.014098	5
0.491282	1.47429	0.583566	2.633944	4.227873	1.12837	3.735909	5
2.124307	2.621508	2.553096	1.81619	1.463642	0.857061	1.801388	3
0.229749	4.356682	3.900132	2.980611	1.59104	2.825456	2.487569	1
0.65872	1.492003	3.98728	1.558729	1.721153	1.716735	2.567419	4
4.311785	3.13258	3.26397	-0.53456	3.583895	0.246863	3.063737	3
1.673673	2.982224	2.381804	0.168301	2.017634	2.223616	2.420761	3
-0.28911	1.117716	3.325504	4.394722	0.710643	2.619891	1.77449	4
-0.40258	1.164411	3.68884	2.699136	3.395212	2.032147	2.131544	5
0.120462	2.660464	3.395254	2.078197	2.900268	0.261296	2.725002	4
1.361992	3.411795	4.64508	0.18819	1.223746	2.532468	1.366811	4

Document: CCI

Author: PPD

Version Number: 0.6

Version Date: 30JAN2023

Template No.: CS_TP_BS016 Revision 6

Reference: CS_WI_BS005

Effective Date: 02Dec2019

3.667904	3.136446	2.321715	2.125103	3.409371	1.537432	-0.2218	3
4.879887	3.475862	2.076838	-0.59349	1.113849	1.688076	0.123996	3
-0.02164	2.41729	2.779121	3.079331	2.108443	1.951256	1.676715	1
-0.3092	2.157215	2.674034	2.803489	1.084307	0.996332	1.994321	4
0.196083	2.475004	2.878793	1.351682	1.201559	0.816825	2.181635	4
0.030238	3.526967	4.532129	0.380547	0.326149	1.986222	1.517082	4
2.275873	2.640193	3.251667	0.839343	2.051567	0.58417	2.170745	3
0.664909	2.042059	2.76595	2.366495	1.440192	0.733822	2.402925	5
1.243306	1.337145	4.074218	2.793057	2.698381	2.51747	3.318289	5
3.22947	2.860181	3.577492	3.502082	2.628584	0.298051	3.390157	5
0.901195	1.663412	2.142304	3.688469	1.330552	2.56257	2.640387	5
2.593164	3.648882	3.709823	3.206283	1.011247	1.094186	3.558644	3
-0.51118	2.448093	2.437806	1.15006	2.797663	3.063268	2.065887	1
-0.11226	1.666885	2.743509	1.415346	0.850013	2.305111	1.401516	4
0.461343	2.627467	4.224476	0.273361	1.87481	0.626399	1.981483	4
2.984818	3.119943	1.817018	0.766638	2.093436	1.529787	0.320228	3
3.77918	4.634406	1.565869	3.283619	0.239241	1.954698	0.044583	2
2.144653	2.782737	3.498727	0.538967	1.545457	0.710868	0.792113	3
0.894321	4.51713	0.328192	4.038478	0.461848	4.202648	0.153093	2
-0.36753	4.43122	3.945508	3.314841	3.447207	2.09228	1.277813	1
-0.54075	4.778543	0.863248	4.518782	2.584591	3.675675	1.102248	1
0.567503	3.24148	3.050335	3.616151	2.485309	1.23559	1.194027	1
-0.14361	3.811718	1.934878	4.106673	2.496619	1.883645	1.255909	1
2.074899	4.309083	3.67494	2.931829	2.158336	1.564656	0.532635	2
-0.19755	3.56726	2.443049	2.469007	2.522924	2.551866	4.876176	1
1.77413	1.53753	2.847139	1.882985	0.272108	1.812518	3.542881	5
1.620442	2.629055	2.66762	-0.09426	2.112038	0.781558	3.528088	3
0.284396	1.770956	2.033619	2.009207	3.469858	0.528655	2.227344	5
3.932854	4.528324	2.861762	1.430475	2.837778	1.200249	2.254885	3
-0.56969	0.692111	4.179689	2.437995	1.95239	1.874127	3.146663	5
4.750689	2.427282	4.856594	3.187711	1.452157	-0.41915	0.793141	3
3.405697	1.355663	3.002656	3.832785	3.044058	1.05007	2.012123	5
3.246586	1.094777	3.274349	3.670523	2.797322	0.536438	3.19334	5
-0.73954	2.073529	3.517236	4.06399	3.114689	3.682423	3.860445	5
-0.52019	1.761008	4.510467	2.327021	2.304678	3.148164	2.974405	4
2.014756	2.407895	2.295336	2.006102	1.24862	3.567501	2.040139	2

 Document: **CCI**

 Author: **PPD**

Version Number: 0.6

Version Date: 30JAN2023

Template No.: CS_TP_BS016 Revision 6

Reference: CS_WI_BS005

Effective Date: 02Dec2019

0.617758	2.661608	1.536687	3.738151	1.672221	2.392486	-0.23323	2
2.207155	1.517604	2.625454	1.804154	0.763335	0.901574	1.873668	3
1.23422	2.210916	2.561197	2.528093	1.527851	1.183324	0.255261	4
0.021092	1.402188	2.331655	1.812051	2.72359	0.272525	2.258971	5
-0.954	5.328812	2.839309	3.194626	2.923765	1.602491	3.133907	1
3.167057	3.125152	1.146554	4.533739	1.648505	1.456163	2.409444	2
0.076614	2.337764	1.24781	1.632617	2.307237	1.494694	0.092505	1
1.769865	3.050355	3.584774	3.050455	0.435454	0.965985	1.414732	4
-0.14345	2.274485	3.363205	2.516223	1.298419	0.84683	0.939489	4
0.73008	2.109659	1.353254	2.267853	1.683644	1.547878	2.385081	1
1.99611	2.845866	2.776477	2.253987	2.519993	1.293208	0.830398	3
0.070748	2.973237	2.458206	2.670777	0.933532	0.498741	0.68469	4
0.876838	1.702267	2.500296	1.205238	1.988358	1.73428	1.88312	5
2.539879	1.866446	1.194986	2.380642	1.503776	2.970662	0.607604	2
1.394134	3.329297	3.029867	2.34767	2.089692	0.610036	3.175958	5
1.370158	3.673851	0.853038	2.542066	2.93799	2.377451	1.666476	1
1.873059	1.656544	2.282509	0.870666	2.632208	0.4312	1.362965	3
2.587309	1.766566	1.972871	2.451865	2.200703	1.026357	0.802177	3
3.83788	1.83301	2.241711	3.814479	1.270124	0.82664	0.010026	3
1.139727	1.009246	2.171023	2.861618	1.94202	1.469105	2.310987	5
0.399375	1.269958	3.185143	3.451366	2.536612	1.873559	3.891391	5
1.155282	0.720076	1.978406	2.550957	1.676011	2.227286	1.931072	5
1.344237	1.329165	2.176408	2.522749	2.36858	1.113254	1.862452	5
1.884397	0.811162	2.366897	3.193561	1.903167	0.529586	3.039549	5
0.857138	1.991846	4.143588	3.203741	2.567467	1.723389	2.662205	5
0.316037	0.913369	3.265191	3.908459	2.02769	2.805904	3.226179	5
0.941557	1.611534	3.550319	2.397795	2.465604	1.637112	2.268425	5
1.001373	0.053415	2.59386	3.243315	2.765545	1.745535	1.070277	5
0.503857	0.731232	2.859462	3.221411	1.999709	0.617281	0.785101	4
0.606582	1.644987	2.617478	3.87998	1.79895	0.52075	1.931541	5
0.028959	0.051636	2.679662	3.743596	1.258786	0.796158	2.684655	5
1.346641	0.874823	2.367707	3.081821	1.922213	0.204586	1.535142	5
1.860828	2.605349	3.667323	4.365784	-0.09249	1.265363	1.238416	2
3.841476	0.719424	2.257701	4.478491	1.331765	0.100831	1.896058	5
1.661837	1.572432	2.894384	4.184757	1.296394	0.92299	2.19499	5
1.639518	1.463103	2.652642	1.584517	2.156156	1.371609	1.96164	5

Document: CCI

Author: PPD

Version Number: 0.6

Version Date: 30JAN2023

Template No.: CS_TP_BS016 Revision 6

Reference: CS_WI_BS005

Effective Date: 02Dec2019

0.422721	1.235118	2.915662	1.806378	1.774961	1.461898	1.782514	5
1.706561	2.255214	2.013119	3.335592	1.432492	1.106246	0.37835	2
1.400759	1.11035	3.176518	2.727226	1.683432	1.484354	2.072159	5
0.261743	1.846856	2.95069	1.604365	1.313196	2.201688	2.045153	4
0.589363	1.63248	2.607093	3.117401	1.985862	1.962965	2.226981	5
-0.25198	1.221123	3.025169	3.361783	1.767464	1.630335	2.390124	5
2.291071	0.293838	3.270165	3.243712	2.442306	-0.00452	2.387481	5
1.537487	0.068818	3.108614	1.546074	2.023246	1.696579	2.706242	5
0.582496	1.908653	2.366867	2.51433	1.475041	0.41553	1.263473	4
2.181457	1.917974	2.429864	2.922081	1.514385	-0.21779	1.973444	3
2.263951	0.29547	3.331314	1.415383	2.346612	1.031364	2.892756	5
2.009356	1.113335	3.138889	3.341652	1.883817	0.109166	1.958678	5
0.172439	1.489999	3.292475	2.720522	1.176231	1.605558	2.641559	5
-0.17314	1.356652	4.442061	3.10633	2.049317	0.791991	1.912506	4
1.388335	1.095188	3.220865	1.628662	1.732311	1.352052	2.405447	5
1.205138	2.024409	3.791492	2.398941	3.006668	1.787416	2.920256	5
0.464397	1.684218	3.40262	2.726862	3.013933	1.189662	3.61535	5
1.628768	1.308049	2.95217	2.745054	1.327077	2.028925	3.357957	5
0.586597	2.536766	2.916748	3.252801	2.392646	2.207333	3.37449	5
0.668672	0.21496	3.401807	3.499059	2.747658	2.264928	3.708938	5
1.85842	1.032293	3.81473	3.017692	2.560804	1.060393	2.687179	5
0.421477	1.193203	3.072718	3.197042	2.410182	2.327653	3.342285	5
0.705007	2.094874	1.758942	2.993589	1.631168	1.769052	2.175233	1
1.341319	2.511154	2.487053	0.737579	1.309727	1.172314	2.21039	3
-0.10475	3.201991	2.494132	3.312053	0.911785	2.561984	0.543735	2
1.26418	1.34083	2.50963	3.164473	0.66512	1.883488	1.486237	2
2.135516	2.140969	2.155306	4.111724	2.433874	1.272746	2.910099	5
0.11181	3.029033	2.241817	4.074078	2.229162	1.485626	1.801666	1
0.57075	4.309476	3.042631	3.640668	1.121444	1.676763	0.985236	2
2.368828	2.078152	1.757995	3.68918	2.238158	0.832056	3.202517	5
0.460592	3.343601	1.369653	3.591892	3.052149	1.590111	1.853283	1
1.039519	2.73413	2.797452	4.794559	3.188477	1.32171	2.069804	1
-0.10856	3.283553	2.221476	2.861392	2.916771	1.670176	1.495856	1
1.635721	1.670994	2.776531	3.481021	3.648923	1.09168	3.517521	5
-0.28728	1.550428	3.027047	1.569179	3.495302	1.675143	3.72542	5
0.629977	1.356138	4.076404	1.705047	2.22813	1.423955	2.063269	4

Document: CCI

Author: PPD

Version Number: 0.6

Version Date: 30JAN2023

Template No.: CS_TP_BS016 Revision 6

Reference: CS_WI_BS005

Effective Date: 02Dec2019

2.307646	2.236448	2.680489	0.969736	2.569013	-0.08536	2.277701	3
2.477069	3.263651	2.163565	2.139497	1.721061	-0.00358	0.65799	3
1.243638	2.913075	4.107979	2.66461	0.995093	-0.14437	1.22687	4
0.527388	1.958446	1.279965	3.081775	0.643036	1.853639	2.172642	1
0.424628	2.137735	2.088917	1.156878	1.766872	1.219234	1.53977	1
2.527044	0.76957	4.013747	2.360512	3.03441	-0.3789	4.007144	5
-0.19304	1.261063	2.340497	2.776243	2.052291	1.922053	3.962693	5
0.533501	1.87061	4.417346	2.075672	3.323951	-0.27006	4.225107	5
2.411661	1.882853	4.355587	1.036112	1.98607	0.055844	1.311082	3
-0.48578	1.752793	4.45535	3.947321	1.094441	2.902358	2.033406	4
0.464869	3.413253	2.635796	2.121825	2.8906	1.996746	3.22642	1
4.132441	0.401081	2.381923	3.456109	0.953315	3.096096	0.555434	2
0.218247	3.435941	1.849422	1.196065	2.511003	1.363478	0.35237	1
-0.32981	4.544489	1.360392	3.024887	1.106194	2.727317	0.572736	1
0.544813	4.282196	2.116876	2.290366	2.541964	1.369559	1.818978	1
-0.47234	4.088985	0.577244	2.967936	2.63388	2.877609	2.381399	1
-0.55527	4.84008	1.960686	2.982342	2.094423	1.626178	1.184506	1
0.263513	3.736018	1.959549	1.758239	1.640343	1.004376	1.472666	1
0.705893	3.718196	2.301378	0.926439	1.774488	0.994932	1.79793	1
0.069405	3.026261	2.43983	3.17107	3.19792	2.883761	1.97275	1
-0.32695	0.330879	2.510527	3.441654	2.057765	2.304866	2.878307	5
2.690017	0.693133	1.730133	3.88509	2.562458	1.455035	1.213344	5
0.46547	1.287936	2.939181	1.394492	3.396399	2.015295	2.080734	5
1.394982	1.559578	2.471032	3.161232	2.57522	0.992441	2.406263	5
0.672309	2.393359	1.896502	2.598218	0.993053	3.154678	1.696235	1
1.693716	1.325886	0.880014	5.37448	1.164323	3.653433	2.895248	5
1.356159	2.406733	2.037301	2.919935	1.869511	3.465406	1.13788	2
1.027015	1.062603	0.659294	4.357499	2.82001	3.266347	4.132878	5
1.436698	-0.58649	1.964863	3.95011	3.191804	0.377813	4.488555	5
4.058956	-0.66886	1.317517	4.606702	1.160914	2.731827	3.099033	5
1.416783	1.490505	2.933091	1.730763	3.560499	0.430518	2.821162	5
0.824231	-0.19387	4.748215	0.202208	2.896445	0.69977	4.873985	5
-0.36924	2.678109	3.163096	1.596358	0.59506	3.346233	1.61617	4
2.327808	1.715927	3.390249	3.327197	-0.07099	1.647033	1.876406	2
1.146957	1.732186	2.467294	4.312694	0.967439	3.606223	2.364763	2
-0.08434	2.371234	1.923559	2.551661	2.780099	-0.41496	2.607441	5

Document: CCI

Author: PPD

Version Number: 0.6

Version Date: 30JAN2023

Template No.: CS_TP_BS016 Revision 6

Reference: CS_WI_BS005

Effective Date: 02Dec2019

2.330935	1.249285	1.977942	-0.29365	1.750854	1.887952	3.34313	5
-0.29097	2.579936	4.03501	2.453226	1.223345	1.756084	1.578965	4
2.433418	1.586402	2.744031	2.943148	2.595221	-0.15045	4.456784	5
1.686219	2.133575	3.063004	2.625084	1.837615	0.138859	2.505072	5
2.182811	2.480894	3.512331	2.528045	3.359501	1.174893	2.358992	5
1.726701	2.611469	3.08875	2.914048	3.581237	1.05601	1.522262	1
0.604793	3.12306	2.124151	2.637198	2.7244	2.472494	1.200589	1
3.236433	3.290153	2.702033	2.314023	3.316992	0.3816	1.895082	3
1.425043	3.692046	3.472158	4.057196	2.405972	0.434079	2.869765	1
2.201707	3.084578	2.151076	4.021647	2.182574	2.301893	1.407549	2
1.815693	2.134869	4.303099	4.369005	1.882038	0.949098	1.847457	4
1.20209	3.064755	4.217095	3.649783	2.915971	0.357701	1.225159	4
0.046373	2.916968	4.455808	2.885248	3.107358	0.426352	2.008252	4
-0.01844	3.893585	3.026784	1.817709	0.913144	3.254477	2.670709	1
0.15412	3.328443	1.620771	1.879719	2.673819	2.668971	2.431268	1
-0.07332	4.359244	3.52468	1.723178	0.553973	1.862672	0.970363	4
0.708979	3.65687	2.295132	2.084227	1.178033	3.673556	0.603624	2
1.454947	3.430231	2.232895	2.447069	2.309456	2.631151	2.32591	1
0.583852	3.473869	2.416568	2.141427	0.479351	2.977283	1.947473	2
0.284904	3.74932	2.086627	3.204144	-0.07831	2.28367	1.519997	2
0.882449	3.863615	3.044836	2.195771	-0.10572	1.730727	0.181928	2
0.180445	1.883516	1.562047	2.663036	2.63216	2.250718	2.436309	1
0.378782	2.931791	1.708711	2.980852	2.771396	2.111069	0.610343	1
0.352732	1.89972	2.265854	3.230448	1.11399	1.21381	2.019503	5
-0.07905	1.7187	0.81324	3.213864	2.58132	2.072825	1.596053	1
-0.04268	2.161476	1.854841	2.9067	2.572292	2.05655	3.250114	1
0.532978	3.478254	2.049047	1.952408	2.807302	1.696268	1.824182	1
0.155656	3.999629	3.146047	1.349007	2.792547	1.478153	1.4613	1
0.796148	2.634837	3.132603	3.222581	2.680883	1.854805	2.030157	1
0.86594	2.609557	2.546813	1.751367	1.740951	1.533923	2.228512	1
1.01185	2.816307	2.912837	1.669116	2.542537	1.330716	1.168323	1
1.350645	1.989788	1.74757	3.198019	2.213117	0.804664	1.34773	1
0.349145	2.756305	1.716076	2.68973	2.739907	1.656974	1.623306	1
0.342705	1.679803	1.833402	2.032994	2.960676	1.663841	2.120364	1
1.484201	1.539412	1.50688	2.924464	2.475359	1.705127	1.683536	5
1.562951	3.030532	1.644437	2.014339	1.595521	1.644179	1.164406	1

Document: CCI

Author: PPD

Version Number: 0.6

Version Date: 30JAN2023

Template No.: CS_TP_BS016 Revision 6

Reference: CS_WI_BS005

Effective Date: 02Dec2019

3.029619	2.819386	1.874296	2.742982	1.788343	2.269874	1.542436	2
0.78352	1.877238	2.074483	2.627216	2.240644	2.194709	2.377748	5
0.710665	2.849776	2.364681	1.919057	2.747839	1.648826	1.233827	1
0.798178	2.933791	3.35471	2.705446	0.796685	3.192393	0.488374	2
1.905889	4.839237	3.456346	0.724097	2.164524	0.999083	1.83366	3
-0.42893	2.354318	2.48451	3.358162	0.714569	2.794577	2.607276	1
2.197681	2.953134	3.844426	1.086876	0.80736	-0.01227	2.050991	3
1.175299	4.850591	4.181569	1.539452	1.490182	0.734061	1.239397	4
-0.50935	3.131051	2.46547	2.550862	1.514948	3.740844	1.942203	1
-0.47872	2.432521	2.670089	3.345092	1.896522	3.066479	3.392814	1
1.647404	2.212889	0.922094	2.565279	2.766181	2.737955	1.599062	1
2.466112	2.010557	3.626749	3.847344	2.514457	1.560699	3.442844	5
3.004502	2.637176	2.798804	3.711184	2.463544	1.57843	2.123784	3
1.241437	2.778655	1.589605	2.563038	2.012834	1.91169	3.491985	1
2.391924	2.637746	2.374582	0.755083	2.629425	2.330716	2.941087	3
1.486578	3.128626	2.487837	1.743571	2.003073	1.737516	1.329548	1
2.586535	2.877124	2.287801	2.632841	1.387282	2.363598	2.453764	2
1.66655	2.838318	2.35911	1.973314	1.859279	2.225311	2.915387	1
1.589938	3.65255	2.956482	2.565466	0.975133	1.615948	0.499501	2
1.945618	3.050839	2.514292	3.234862	2.203473	1.822279	1.99805	1
1.755469	2.075945	3.480556	2.94479	1.519334	1.681199	0.758004	4
2.935053	2.718756	3.31552	2.504717	1.889886	1.201849	1.460136	3
2.119775	3.394806	2.506338	2.120552	2.614302	0.679575	0.89525	3
2.458961	2.329016	2.154788	3.310596	1.474675	2.59347	1.591725	2
1.244654	1.73021	1.827923	2.489334	1.383575	2.073081	1.360675	1
-0.20744	1.946772	4.276268	1.584494	1.25229	0.51958	1.276463	4
1.074974	1.973074	1.265671	1.897755	2.948865	0.870864	1.737043	1
-0.14189	-0.04374	3.164932	3.531256	1.980725	0.632499	3.87712	5
3.376984	0.831567	2.275181	2.779673	1.98059	1.308505	1.968036	5
0.410408	1.295473	3.211679	2.991182	2.99265	1.394861	2.979216	5
0.412831	0.728305	2.774347	3.476108	2.485126	0.143779	1.325316	5
0.395383	1.266636	3.547077	3.848593	2.41841	0.233631	1.330153	4
0.303011	0.68115	3.431149	2.896138	2.845076	0.290205	2.987518	5
0.623263	2.844467	2.011102	3.13837	1.748296	2.03984	2.51607	1
0.430849	2.024006	2.387261	2.938496	1.830338	1.725661	1.602135	1
0.302646	3.078668	1.809565	2.02404	2.874748	0.986561	3.022366	1

 Document: **CCI**

 Author: **PPD**

Version Number: 0.6

Version Date: 30JAN2023

Template No.: CS_TP_BS016 Revision 6

Reference: CS_WI_BS005

Effective Date: 02Dec2019

0.217969	2.234125	3.086551	2.801215	2.881359	1.925122	2.6483	1
1.148024	4.715529	1.712537	1.143191	1.448075	0.735696	1.255713	1
0.17321	2.714301	3.093773	2.731845	3.555077	0.30472	1.964692	1
1.628505	1.333563	2.279517	3.023174	2.166503	1.909445	2.062154	5
1.460183	2.173385	1.803192	2.793002	2.444099	0.941715	2.221664	5
0.443037	2.964066	1.915887	2.678915	1.792021	2.577074	1.45575	1
0.462123	1.136766	3.163593	3.69979	3.024302	-0.067	2.09806	5
-0.00933	2.530804	3.25533	3.315988	1.517136	0.677362	2.642933	4
1.040869	1.969233	2.705048	4.084591	2.318205	0.820581	2.483245	5
0.146118	1.409769	2.792843	2.852647	2.966719	0.792185	2.797111	5
0.957539	1.814681	2.711	3.043293	1.665616	0.197362	2.822844	5
1.552961	2.008691	3.036311	3.633731	2.497589	-0.00887	1.003566	4
1.250273	3.122429	2.403355	3.189958	1.795676	0.107745	0.924363	1
1.322036	1.215882	3.921602	3.003509	2.284119	-0.24933	1.806291	5
0.251952	2.113829	2.664782	3.034502	1.648737	0.259419	2.65026	5
0.59895	3.329155	2.836852	2.202842	1.497784	1.607472	2.583754	1
0.565399	5.191211	2.58232	2.271006	2.778369	1.798438	0.76725	1
1.891514	1.030671	2.378489	2.521739	2.470474	1.713408	1.830049	5
2.251343	1.964833	2.782653	2.173102	2.552897	0.928943	2.420509	5
0.827273	1.676045	1.79413	2.599383	2.936736	2.290989	1.069859	1
0.933062	4.872175	1.858903	3.41357	1.483246	3.481183	0.717352	2
1.319798	3.170397	2.467164	3.559172	3.259405	2.329196	0.779611	1
1.159981	2.887268	2.048998	1.864787	1.714485	1.964015	0.851252	1
2.594349	4.47202	1.935226	2.39397	0.807125	1.443819	1.010001	2
2.259674	2.817409	2.241478	3.232779	1.265977	2.904775	1.005764	2
3.853234	3.442007	3.483622	1.254111	2.035139	0.95848	2.220828	3
0.107242	2.316128	1.787862	2.913061	2.647041	1.852659	1.796499	1
4.540121	2.034294	1.273216	4.195778	0.812797	3.901634	2.414239	2
1.940409	1.744759	2.334533	3.048773	2.032325	1.673573	2.156116	5
1.771326	1.136763	2.607683	3.880771	1.931054	1.665451	2.462573	5
2.056638	0.596344	2.676342	3.652917	1.954028	1.575281	2.359132	5
1.998099	1.080433	2.593327	4.200915	1.916664	1.49471	2.380617	5
1.973644	0.455134	3.08072	4.16708	1.829094	1.683288	2.447056	5
1.836602	0.707831	2.460104	4.184537	1.830863	1.615467	2.488581	5
1.970747	1.071085	2.266924	3.64906	3.038635	1.177264	2.83891	5
2.048913	1.390075	2.210913	3.567033	2.003754	1.363302	2.075113	5

Document: CCI

Author: PPD

Version Number: 0.6

Version Date: 30JAN2023

Template No.: CS_TP_BS016 Revision 6

Reference: CS_WI_BS005

Effective Date: 02Dec2019

1.017331	2.182473	3.564923	0.448758	2.352833	2.376049	3.255035	5
1.725945	3.009119	2.694312	0.112874	3.046849	1.046677	2.597689	3
0.631709	2.429373	2.904648	1.845756	1.753777	3.513261	1.93335	1
-0.23163	3.002049	3.345794	2.547498	3.554414	1.593511	3.265845	1
-0.21477	2.923092	2.388016	3.395137	2.936315	2.417217	2.608649	1
2.292153	2.412309	2.891003	2.297742	1.884942	0.821511	1.938632	3
1.826434	3.195578	1.861429	3.285702	2.60437	0.337541	1.982752	1
1.081747	2.024036	3.051124	2.759296	2.689623	2.411139	3.523435	5
1.726368	2.23849	3.132346	2.316369	2.459357	2.194413	2.921579	5
0.273047	2.916457	1.761402	3.342903	1.357142	2.447486	1.642088	1
2.061364	2.246574	2.274476	2.84223	2.513461	1.435599	1.663619	5
-0.44394	1.990884	2.120804	2.786634	1.973897	3.156599	3.453843	1
0.965206	1.901004	1.431642	3.042105	2.183742	2.33692	2.365446	1
1.658993	1.392341	3.179016	2.725544	1.270456	1.609023	2.18851	5
1.841815	2.190828	2.24286	3.811443	2.195616	0.758591	2.922796	5
1.22653	1.421029	2.261803	2.765931	2.425561	1.732311	3.372288	5
-0.23487	2.062772	2.559663	2.79011	1.445805	2.657801	2.760422	1
0.245227	2.689176	1.443797	1.973458	2.887213	1.25989	2.374189	1
2.215864	1.754762	2.859705	4.169328	2.445922	1.18503	2.197257	5
2.827656	1.672037	1.272949	2.704282	2.616846	2.725432	3.720687	5
3.199189	1.422016	2.654105	4.302128	3.544407	1.718565	4.051834	5
2.403098	2.968469	4.036389	2.438671	1.294979	0.563823	1.703829	3
2.45239	3.234068	2.759748	1.024698	1.562684	1.112423	2.375853	3
1.502019	2.281229	1.340381	1.610793	2.423306	1.047639	1.624365	1
1.77479	1.921922	3.237566	1.352774	2.492678	1.049467	2.512043	5
1.663432	3.019771	1.897049	0.759906	3.501306	1.569326	1.914466	1
2.94352	2.35016	2.281449	0.951598	2.511059	1.019162	1.526363	3
1.68009	2.045579	1.887194	2.357748	1.978092	1.635593	2.811834	5
0.808124	-0.13738	2.953735	3.906694	1.947323	1.380431	2.901026	5
1.209549	-0.67634	4.084019	3.428157	1.289318	1.264035	2.480664	5
1.733745	-0.34144	2.996359	2.729753	1.784482	-0.03631	2.462543	5
1.619052	0.150902	4.359022	2.334887	2.914195	-0.11285	1.33825	5
-0.13043	0.923062	2.34262	2.347549	0.138352	3.16152	1.597485	4
1.32315	0.012205	4.865486	0.779994	1.714469	0.367159	2.011743	4
2.650652	1.224055	2.722871	2.274911	1.37163	1.630707	1.845764	3
1.607415	2.287416	2.580634	1.22177	2.238811	1.518263	0.841124	3

Document: CCI

Author: PPD

Version Number: 0.6

Version Date: 30JAN2023

Template No.: CS_TP_BS016 Revision 6

Reference: CS_WI_BS005

Effective Date: 02Dec2019

0.407971	0.974984	2.534841	2.228252	3.585527	2.013955	3.485656	5
1.576527	1.697772	2.575915	3.470199	2.282271	1.37511	2.962369	5
1.956178	-0.46028	4.546977	2.448721	1.334782	1.148109	3.918205	5
0.18701	2.273386	4.282304	2.119968	2.185045	2.674903	1.84133	4
0.354561	1.314933	4.056158	2.91016	1.719733	1.791516	-0.16259	4
0.797993	0.857493	3.688851	3.229713	3.474734	2.372434	1.533996	5
1.856804	2.053879	1.920647	2.220341	2.898173	0.918768	1.764507	5
-0.13872	3.299856	3.489781	2.220536	1.711955	1.704413	3.085852	1
0.72802	2.655034	3.106166	2.872185	1.647015	1.176479	0.846061	4
0.225626	1.874406	1.825989	3.058365	2.868861	3.509008	2.042135	1
2.051621	1.818373	4.017949	2.104391	1.201151	0.575975	1.724579	3
0.59504	1.95428	5.204595	1.783968	1.497278	1.731733	1.678559	4
1.584827	0.935282	3.327166	1.94125	2.179968	0.358369	3.245291	5
0.928618	0.658035	3.076131	3.113168	2.172916	1.004145	3.430131	5
2.201803	1.135876	4.001561	1.791912	1.757235	0.255488	2.840382	5
3.807773	3.594538	1.889844	0.931891	1.714179	-0.22761	0.176671	3
0.242025	1.84378	3.468098	2.711658	2.422419	0.129613	1.804384	4
2.001564	1.682021	3.01414	2.000518	1.811704	0.298292	1.451765	3
1.563126	0.95651	2.505286	2.57955	1.915208	0.43884	3.595415	5
0.166357	2.392899	3.069375	2.770552	1.708797	3.004771	0.534774	1
0.537015	2.481759	5.567584	0.735376	1.212872	0.596699	1.804847	4
1.419943	3.311596	2.146657	1.1977	1.445532	1.588575	0.49374	3
1.6282	2.717846	3.449848	2.08389	0.548107	3.320778	3.109258	2
0.74564	4.329717	3.465316	2.586558	0.874382	2.331343	0.952736	2
-0.53777	2.184301	1.465823	2.443865	3.215783	3.614718	3.522195	1
0.517961	4.639776	1.693983	2.760274	1.535191	2.33917	2.777603	1
3.464622	3.305747	3.148404	1.874921	1.356197	0.483571	0.587682	3
1.831054	3.21794	1.980434	1.148194	2.693122	0.351515	2.311651	3
1.334201	2.45268	3.196957	1.766991	1.617076	0.218062	2.178214	4
1.925363	1.20103	1.434322	1.670427	2.831532	1.924301	2.443715	5
2.379776	1.265335	2.872741	2.090623	3.297923	2.679207	2.677931	5
-0.50069	3.784005	2.725673	3.553338	0.042037	2.158042	2.048815	2
0.315685	2.035559	1.810852	3.164387	0.491681	3.110445	2.98571	1
1.791176	1.005473	2.139767	2.53269	1.78994	2.214137	2.723798	5
1.979567	1.748545	1.776153	2.846214	2.002051	1.003302	2.429969	5
1.853418	3.53585	3.835734	0.856978	1.400599	3.712702	2.91704	1

 Document: **CCI**

 Author: **PPD**

Version Number: 0.6

Version Date: 30JAN2023

Template No.: CS_TP_BS016 Revision 6

Reference: CS_WI_BS005

Effective Date: 02Dec2019

1.63315	1.316722	2.619318	2.937318	1.916679	1.496701	3.180816	5
1.884768	1.551881	2.123122	4.401792	3.459827	1.945	2.269949	5
3.020426	2.411129	2.633178	2.075542	1.667037	2.194526	2.91346	3
1.449371	3.431235	3.018328	1.125531	3.259058	1.10168	1.764484	3
0.84953	1.932868	3.02034	1.862252	3.688928	2.444511	1.698493	1
2.228413	1.91244	2.305406	2.513044	2.202764	1.670849	3.270545	5
1.208468	2.707595	4.269007	2.566786	2.451727	1.520423	1.423032	4
2.061931	1.903822	2.856964	2.327123	1.620568	0.117391	1.840711	3
